16.9 Protocol Amendments

The investigators will conduct the study in compliance with the protocol given approval/favourable opinion by the Ethics Committee and the Regulatory Authority. Changes to the protocol may require regulatory authority/ethics committee approval/favourable opinion prior to implementation, except when modification is needed to eliminate an immediate hazard(s) to patients. The CTU in collaboration with the sponsor will submit all protocol modifications to the competent authority/research ethics committees for review in accordance with the governing regulations. Protocol compliance will be monitored by the CTU who will undertake site visits to ensure that the trial protocol is adhered to and that necessary paperwork (e.g. CRF's, patient consent) is being completed appropriately.

16.10 Patient Confidentiality

In order to maintain confidentiality, all study reports and communication regarding the study will identify the patients by the assigned unique trial identifier only.

Computers where information will be stored will be password protected. Patient confidentiality will be maintained at every stage and will not be made publicly available to the extent permitted by the applicable laws and regulations.

16.11 Post-trial Care

Once the trial is completed, patients who participated in the study and who still present with DMO will revert to the NHS standard of care. If no DMO is present, observation will be recommended.

16.12 Record Retention

The PI will be provided with an ISF by the CTU and will maintain all trial records according to GCP and the applicable regulatory requirements. The Trial Master File (TMF) will be held by the CTU within the BHSCT and the essential documents that make up the file will be listed in an SOP. On completion of the trial, the TMF and study data will be archived by the CTU according to the applicable regulatory requirements and for up to 15 years as required by the BHSCT Sponsor. Following confirmation from the Sponsor the CTU will notify the PI when they are no longer required to maintain the files. If the PI withdraws from the responsibility of keeping the trial records, custody must be transferred to a person willing to accept responsibility and this must be documented in writing to the CTU and Sponsor.

17. DISSEMINATION/PUBLICATIONS

17.1 Trial Publications

The final study report will be provided by the Trial Statistician; it is anticipated that the study findings will be published in national and international peer review journals which will be led by the CI. This will secure a searchable compendium of these publications and make the results readily accessible to the public and health care professionals. In addition study findings may be presented at both national and international meetings and also to appropriate patient groups.

Upon request, patients involved in the trial will be provided with a lay summary of the principal study findings. The most significant results will be communicated to the public through press releases. An on-going update of the trial will also be provided on the NICTU website.

17.2 Authorship Policy

An author will be considered to be someone who has made a substantive intellectual contribution to the study. All investigators, Trial Statistician and relevant members of the Trial Management Group will potentially be co-authors. Contributors from Araim Pharmaceuticals Inc. will also be co-authors. Collaborators will be acknowledged.

17.3 Trial Registration

The trial will be registered with the European Union Drug Regulating Authorities Clinical Trials (EudraCT) database and the International Standard Randomised Controlled Trial Number (ISRCTN) register.

17.4 Data Sharing Statement

The trial data will be shared with Araim Pharmaceuticals Inc.

17.5 Data Access

Following the publication of the primary and secondary study outcomes, there may be scope to conduct additional analyses on the data collected. In such instances formal requests for data will need to be made in writing to the CI who will discuss this with the TMG. In the event of publications arising from such analyses, those responsible will need to provide the CI with a copy of any intended manuscript for approval prior to submission. Authorship will need to take the format of "[name] on behalf of the ARA 290-DMO Clinical Trial Group" or something similar which will be agreed by the TMG.

1. BACKGROUND AND DESIGN

The hypothesis tested is that ARA 290, when administered subcutaneously at 4mg on a daily basis for 12 weeks, due to its anti-inflammatory, anti-apoptotic and neuroprotective effects, will be of therapeutic value to patients with diabetes mellitus and diabetic macular oedema.

This will be an interventional, exploratory, investigator led, pilot study with the aim of determining if ARA 290 administered at a daily dose of 4mg subcutaneously for 12 weeks to patients with DM and severe DMO (central retinal subfield thickness measured with spectral domain optical coherence tomography of \geq 400 microns), will have a beneficial effect on improving BCVA, reducing central subfield thickness, increasing central retinal sensitivity and retinal perfusion, increasing tear production and improving quality of life with no adverse events. Data obtained in this pilot study will be used to inform future larger studies.

The primary objective is to determine whether ARA 290 has a beneficial effect on BCVA in people with DM and DMO.

The secondary objectives are to determine whether ARA 290 administered at a daily dose of 4mg subcutaneously for 12 weeks to patients with diabetes mellitus and DMO can improve vision (as determined by the % of participants with a \geq 10 and \geq 15 ETDRS letter gain), reduce central subfield thickness, increase central retinal sensitivity, increase tear production and improve retinal perfusion and quality of life with no deleterious side effects. The effects of ARA290 on the systemic and metabolic control of participants will be also evaluated in an exploratory manner.

ARA 290 antibodies will be determined as, if they were to develop in people undergoing this treatment they could have an impact on the potential subsequent response to it.

Inflammatory markers will be evaluated to investigate the potential anti-inflammatory effect of this treatment. Carbamylated albumin will be obtained as an additional measure of renal function and metabolic status and glycosylated albumin will be obtained as a confirmatory marker of glucose control.

This is a prospective, open label, interventional, single centre, investigator led, phase II study to examine the effect of ARA 290 on DMO in patients with type 1 or 2 diabetes and central retinal subfield thickness of \geq 400 microns.

The study intervention is a subcutaneous daily administration of ARA 290 in a dose of 4mg for 12 weeks

Patients will be eligible to participate in the study if they fulfil the following criteria:

Inclusion criteria:

[figure not shown]
- 1. Diabetic retinopathy and centre involving DMO with a central subfield thickness of \geq 400 microns, as determined using SD-OCT.
- 2. \geq 18 years of age
- 3. Clear media and naïve to previous treatments for DMO

Exclusion criteria:

- 1. Macular oedema related to other retinal disease
- 2. Hazy media that prevents adequate retinal imaging
- 3. Allergy to fluorescein
- 4. Previous treatments for DMO
- 5. DMO with central subfield thickness of < 400 microns
- 6. Patients on local or systemic steroids
- 7. Use of erythropoiesis stimulating agents within the two months prior to screening or during the trial
- 8. Treated with any other investigational medication or device within 60 days
- 9. Pregnant women, women who have not yet reached the menopause (no menses for ≥ 12 months without an alternative medical cause), who test positive for pregnancy, or who are unwilling to take a pregnancy test prior to trial entry or are unwilling to undertake adequate precautions to prevent pregnancy for the duration of the trial.
- 10. Men who have a female partner and who are unwilling to undertake adequate precautions to prevent pregnancy for the duration of the trial.
- 11. Female patients who are breastfeeding will be excluded.
- 12. Active proliferative diabetic retinopathy (PDR) requiring treatment.
- 13. Patients with other eye diseases besides diabetic retinopathy
- 14. Patients who are unable or unwilling to commit to the study schedule of events
- 15. Serious illness that is likely to affect the patient's ability to complete the study

Any patient showing a clinically significant improvement between the initial screening and presenting for the first screening/baseline visit may no longer be eligible for the study and will be recorded as a screen failure and will not be entered on to the study.

The trial is summarised in Figure 1.

Full details of the background to the trial and its design are presented in the protocol.

2. OUTCOME MEASURES

2.1 Primary outcome measure

Changes from baseline to week 12 (+/-7) days in best corrected distance visual acuity.

2.2 Secondary outcome measures

Changes from baseline to week 12 (+/-7) days in:

- 1. Central subfield thickness
- 2. Central retinal sensitivity
- 3. Retinal perfusion
- 4. Tear production
- 5. Patient reported outcomes
- 6. ARA 290 antibodies

Adverse events

% of participants with ≥ 10 ETDRS letter gain

% of participants with ≥ 15 ETDRS letter gain

2.3 Exploratory analyses

Changes from baseline to week 12 (+/-7) days in:

- 1. Inflammatory markers
- 2. Carbamylated and glycosylated albumin

2.4 End of trial

For the purposes of submitting the end of trial notification to the Sponsor, MHRA and REC the end of trial will be considered to be when database lock occurs for the final analysis. The trial will be stopped prematurely if:

- Mandated by the Research Ethics Committee (REC)
- Mandated by the Medicines and Healthcare products Regulatory Agency (MHRA)
- Mandated by the Sponsor (e.g. following recommendations from the Data Monitoring and Ethics Committee (DMEC)
- · Funding for the trial ceases

The REC that originally gave a favourable opinion of the trial and the MHRA who issued the Clinical Trial Authorisation (CTA) will be notified in writing once the trial has been concluded or if terminated early.

3. DATA

3.1 CRF Forms and variables

Full details of the data to be collected and the timing of data collection are described in the trial protocol.

A copy of the CRF is presented in the Trial Master File.

3.2 Data completion schedule

The following table describes the time points for completion of clinical record forms.

Table 1. Data Completion Schedule

	Screening / Baseline	2 week s	4 weeks	8 weeks	12 weeks	16 weeks*	4 weeks post drug termination**
Consent	✓						
Pregnancy Test	✓						
Medical History	✓		√	√	√	✓	
Medications	✓		√	√	√	✓	
Vital Signs***	✓		√	√	√	√	
Distance Visual Acuity	✓		√	√	✓	√	
Microperimetry	√				✓	√	
Schirmer Test	√				✓	√	
SD-OCT	√		✓	✓	✓	✓	
Wide-angle FFA	✓				✓		
Blood sample for ARA 290 antibodies, immune markers, carbamylated and glycosylated albumin	✓				✓		
Blood sample for full blood cell count	~				√	✓	
Liver function test (LFT)	~				✓	√	
Urine Sample	✓				✓	✓	
Adverse Events		✓	√	✓	✓	√	✓
VFQ-25	~				✓	√	
EQ-5D-5L	~				✓	√	
C-SSRS	~		✓	✓	✓	√	
Telephone check		√					✓

- * 16 week visit will take place only if the retina is found to be dried and the DMO has resolved at week 12
- ** 4 week post study drug termination telephone check will be completed for patients who withdraw from the trial/study drug prior to 12 weeks, or at 12 weeks, and who do not need to attend the 16 week visit.
- *** Vital signs: height (first visit only); weight; heart rate; temperature; blood pressure, oxygen saturation, BMI

3.3 Data verification

Data verification, consistency and range checks will have been performed at the data entry stage by the CTU, as well as checks for missing data (copies can be found in the Trial Master File). Additional range, consistency and missing data checks will be performed, as appropriate, when the analysis is performed (and when the datasets for analysis are constructed). All variables will be examined for unusual, outlying, unlabelled or inconsistent values.

Given the thorough nature of our follow-up procedure we expect the issue of missing data to be relatively minimal. We anticipate high compliance with initial data collection as this is close to the time of patient registration. If any data is missing imputation will not be done.

Any problems with trial data will be queried with the Trial Managers, Data Managers, or statisticians, as appropriate. If possible, data queries will be resolved, although it is accepted that due to administrative reasons and data availability a small number of problems will continue to exist. This will be minimised.

3.4 Data coding

The variable codings will be as specified on the CRF.

3.5 Management of datasets

Below is the standard policy for management of data in the CTU as given in the CTU SOPs.

At the time of final analysis:

The trial database will be stored in MACRO:

- In collaboration with the Statistician, the Data Manager will file out from MACRO a
 dataset of all data stored in the database. This will act as the frozen dataset. It is the
 responsibility of the statistician to accurately record the date of freezing and ensure all
 data is retrieved.
- If any outstanding data queries are resolved during the analysis that relate to data in the frozen dataset (e.g. problems that are found during analysis or amended CRFs that are returned to the CTU), the main MACRO database should be changed under the oversight of the Trial Data Manager.

4. **DEFINITION OF TERMS**

Give definition of any terms that require explanation.

Term	Definition
Best corrected	Best corrected distance visual acuity will be obtained in both eyes by a
distance visual	trained optometrist using the Early Treatment Diabetic Retinopathy Study
acuity (BCVA)	(ETDRS) charts at baseline and at weeks 4, 8 and 12. If at week 12 the
	retina is dry, a further visit at week 16 will be undertaken and BCVA will be
	obtained at this visit. The EDTRS total score will be recorded and used for
	the analysis.
Central	Central subfield retinal thickness (CST), as obtained in the central 1 mm
subfield retinal	
thickness	area, will be determined by spectral domain optical coherence tomography
UTICKTIESS	(SD-OCT) and used for the analysis. In addition, presence or absence of
	intraretinal or subretinal fluid will be evaluated and recorded in the
	appropriate CRF. SD-OCT will be obtained in both eyes by an ophthalmic
	photographer at baseline and weeks 4, 8 and 12. If at week 12 the retina is
	dry, a further visit at week 16 will be undertaken and SD-OCT obtained at
	this visit.
Retinal	Retinal perfusion will be assessed by wide angle fundus fluorescein
perfusion	angiography (FFA). Wide-angle fluorescein angiographic images will be
	obtained by an ophthalmic photographer with the help of a research nurse at
	baseline and at the week 12 visit. The FFA run will be obtained from the
	study eye; images in the fellow eye will also be obtained at arterio-venous
	and later phases of the angiogram.
	Wide angle FFA results will be evaluated qualitatively for the
	presence/absence and extension of areas of retinal ischaemia. The FFA
	obtained at the 12 week follow up visit will be compared with that obtained
	at baseline to determine the existence of new areas of ischaemia and the
	increased/reduced size of pre-existing areas of ischaemia.
	In addition it is planned that areas of retinal ischaemia will also be detected
	and quantified automatically using an ImageJ program developed by our
	group. This software uses a combination of four binary masks, calculated
	independently, to adapt the detection of ischemic areas to different regions
	of the image. Images will be evaluated by an investigator masked to the
	participant and the study visit. Total area of ischaemia will be determined
	and used for the analysis.
Retinal	Retinal sensitivity will be determined by macular microperimetry in both
sensitivity	eyes. Microperimetry will be undertaken by an optometrist at baseline and at
	12 weeks. If at week 12 the retina is dry, a further visit at week 16 will be
	undertaken and macular microperimetry obtained.
	Mean sensitivity in the central 10 degrees of the retina will be recorded and
	used for the analysis.
Schirmer test	The Schirmer test will be performed to measure tear production. The test will
	be undertaken by a Research Nurse at baseline and at week 12. If a further
	visit at week 16 is undertaken, this test will be also performed at this
	additional visit. This is a safe test which poses no risk to the patient. A
	negative test result is normal i.e. more than 10mm of moisture on the filter
	paper in 5 minutes. As both eyes normally secrete the same amount of tears,
	this test will be only done in the study eye (see Statistical Considerations
	section). This test will be done following completion of all functional tests
	,
	(i.e. BCVA and microperimetry). This test is included as patients with DR

	often complain of dry eyes, most likely related to reduced corneal nerve fibre density. Given the effect of ARA 290 in increasing corneal nerve terminals observed in previous studies, we plan to evaluate whether tear film production may improve following this treatment. The millimetres of moisture on the filter paper for each eye will be recorded and used for the analysis
Patient reported outcomes	Patient reported outcomes will be evaluated by means of EQ-5D 5L and NEI VFQ-25 questionnaires which will be administered to patients at baseline and at week 12 (and at week 16 if applicable). The NEI VFQ-25 is a vision specific patient reported quality of life tool. This validated questionnaire has been used widely to evaluate visual outcomes in patients with eye diseases including DR. In addition to eliciting information about general health and vision it specifically addresses difficulty with near vision, distance vision, driving and the effect of light conditions on vision. This provides a comprehensive evaluation of vision related quality of life. A generic health status measure EQ-5D-5L will be used to generate utility data. Total scores will be recorded and used for the analysis. Suicidal ideation will be assessed using the Columbia Suicide Severity Rating Scale (C-SSRS) which will be administered to patients at baseline and weeks 4, 8 and 12. If at 12 weeks the retina is dry a further visit at week 16 will be arranged and questionnaires completed.
Blood/Urine Samples	A blood sample (34 mls (approximately 2 tablespoons)) and a urine sample will be taken at baseline, 12 weeks (and 16 weeks if the macular oedema resolved at week 12). The urine sample and part of the blood sample will be used to test for the following: • Pregnancy Test • Full blood cell count • CBC with reticulocytes • HbA1c • Glucose • Lipid profile (HDL, LDL, triglycerides) • C peptide levels • Creatinine clearance • Albumin excretion rate • Liver function test (ALT and AST)

5. SAMPLE SIZE CALCULATIONS

This will be an early phase, open label, interventional pilot study to evaluate the potential beneficial effect of ARA 290 for the treatment of patients with DR and DMO and further assess the safety of this treatment. Ten patients will be recruited. A sample of this size is expected to be sufficient to provide an indication of a potential beneficial effect of the drug on the outcomes investigated and further information on safety of ARA 290 in a diabetic population. Data obtained in this study will be used to inform future larger studies.

6. ANALYSIS PRINCIPLES

In participants in whom both eyes are eligible for inclusion into the study, the eye with the better BCVA will be used as the study eye; however data will be collected and evaluated for both eyes.

Descriptive statistics will be used for the evaluation of primary and secondary outcomes. Differences in mean (SD) change from baseline for all the continuous variables investigated including visual acuity, central subfield thickness, area of retinal ischaemia, retinal sensitivity, patient reported outcome scores as well as levels of ARA 290 antibodies. Confidence intervals will also be presented. When data is not normally distributed, median (interquartile range) will be presented.

Adverse events will be presented using counts and percentages. Additionally, the % of participants with 10 or more and 15 or more ETDRS letter gain will be also reported. Data obtained at week 16 would have been similarly evaluated; however no patients required a 16-week visit.

Exploratory analysis in relation to inflammatory markers and carbamylated and glycosylated albumin will also be observed from baseline to the week 12 visit.

If the retinal perfusion image analysis is not available, it may be presented in a later report.

Additional analysis (not specified in the protocol) will be performed to explore the treatment effect in the non-study eye for (a) those patients with DMO in the non-study eye that did not fulfil the criteria for inclusion into the study (e.g. in patients with central retinal subfield thickness of < 400 microns or in patients with non-central involving DMO) and (b) patients with DMO in the non-study eye that fulfilled criteria for inclusion into the study (e.g. ≥ 400 microns).

As the analysis is only descriptive, no imputation or sensitivity analysis will be performed.

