Similarly, the first in human studies comprising intravenous administration of a single ascending dose and multiple ascending dose in healthy volunteers, single intravenous and subcutaneous cross-over study in healthy volunteers and in subjects with renal impairment, and intravenous repeat dose in end-stage renal disease subjects undergoing haemodyalisis raised no safety concerns. Furthermore, studies using intravenous and subcutaneous administration of ARA 290 to patients with sarcoidosis [19, 20] and type 2 diabetes mellitus [21], including studies using the same dose and route as that proposed in the current study (4 mg subcutaneous administration of ARA 290), as well as studies in patients with critical limb ischaemia, and rheumatoid arthritis have supported further the safety profile of ARA 290. No allergic reactions have been observed to ARA 290.

Specifically, two studies have been previously conducted in people with type 2 diabetes mellitus, pre-diabetes and/or drug-naïve type 2 diabetes. In both, a daily subcutaneous 4 mg dose of ARA 290 administered during a 4 week period was used. In these studies 24 and 12 patients, respectively, received ARA 290 (24 and 12 received placebo, respectively). At the dosage used, ARA 290 appeared to be safe. Adverse events were generally mild; the most common being gastrointestinal issues, sleep disturbance and headache; the frequency of adverse events was similar in both ARA 290 and placebo groups.

The dose and route of 4 mg was chosen for the current study as pharmacokinetic studies using ARA 290 demonstrated that a daily subcutaneous dose of 4 or 6 mg of ARA 290 resulted in consistent blood levels above 1-2 nM, the minimum projected exposure for efficacy [18]. The current phase 2 study however, entails for the first time prolonging the duration of treatment, from 28 days, as used in most previous studies, to 84 days. The three month duration of the ARA 290 dosage was chosen as it is expected that if treatment were to be beneficial, functional and anatomical improvements could potentially be detected in this time period but may not be seen earlier, as only patients with severe DMO (central retinal thickness of \geq 400 microns) will be included in this investigation. Furthermore, it is unlikely that a detrimental effect on vision will be observed by postponing anti-VEGF treatment for this length of time [22]

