4.3 Study Objectives

4.3.1 Primary Objective:

To determine whether ARA 290 has a beneficial effect on BCVA in people with DM and DMO.

4.3.2 Secondary Objectives:

The secondary objectives are to determine whether ARA 290 administered at a daily dose of 4mg subcutaneously for 12 weeks to patients with diabetes mellitus and DMO can improve vision (as determined by the % of participants with $a \ge 10$ and ≥ 15 ETDRS letter gain), reduce central subfield thickness, increase central retinal sensitivity, increase tear production and improve retinal perfusion and quality of life with no deleterious side effects. The effects of ARA290 on the systemic and metabolic control of participants will be also evaluated in an exploratory manner.

ARA 290 antibodies will be determined as, if they were to develop in people undergoing this treatment they could have an impact on the potential subsequent response to it.

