Mean ±SD presented for continuous variables (or median [interquartile range] when appropriate) and no. (%) for categorical variables.

Data listings for the visual outcomes will be included as an appendix in the final statistical report.

Table 3.4 Exploratory Analysis (All Eyes with DMO >400 Microns)

		All Eyes with DMO ≥ 400 Microns						
		Baseline		Week	(12	Chang	је	
		n = (%)		n = ((%)	n = (%)		
Primary outcome; best corrected distance visual acuity		xx.x ± xx.x		xx.x ± xx.x		xx.x ± xx.x		
Central sub thickness (r		xx.x ± xx	.x	xx.x ± xx.x		xx.x ± xx.x		
Central reti (dB)	nal sensitivity	xx.x ± xx	.x	xx.x ± xx.x		xx.x ± xx.x		
	Macular Ischaemia	Present Absent N/A	n(%) n(%) n(%)	Present Absent N/A	n(%) n(%) n(%)	Extension Reduction No change N/A	n(%) n(%) n(%) n(%)	
Retinal perfusion	Foveal Ischaemia	Present Absent N/A	n(%) n(%) n(%)	Present Absent N/A	n(%) n(%) n(%)	Extension Reduction No change N/A	n(%) n(%) n(%) n(%)	
	Peripheral Ischameia	Present Absent N/A	n(%) n(%) n(%)	Present Absent N/A	n(%) n(%) n(%)	Extension Reduction No change N/A	n(%) n(%) n(%) n(%)	
	Total area of ischaemia	xx.x ± xx.x		xx.x ± xx.x		xx.x ± xx.x		
% of participants with ≥ 10 ETDRS letter gain		-		-		n(%)		
% of partic	ipants with ≥ RS letter gain	-		-		n(%)		

Table 4.1 Safety Outcomes

		ARA290 n= <n></n>
AEs,	Total number of Adverse Events (AEs)	n
SAEs	Number of patients experiencing an AE	n (%)
and	Total number of Adverse Reactions (ARs)	n
SUSARs	Total number of Serious Adverse Events (SAEs)	n
	Number of patients experiencing an SAE	n (%)
	Total number of Serious Adverse Reactions (SARs)	n
	Total number of events related to study drug and unexpected (SUSARs)	n
	Total number of Deaths	n (%)
AE	General disorders and administration site conditions	n (%)
	Vascular disorders	n (%)
	Eye disorders	n (%)
	Gastrointestinal disorders	n (%)
	Psychiatric disorders	n (%)
	Metabolism and nutrition disorders	n (%)
	Infections and infestations	n (%)
	Nervous system disorders	n (%)
	Musculoskeletal and connective tissue disorders	n (%)
	Injury, poisoning and procedural complications	n (%)
	Respiratory, thoracic and mediastinal disorders	n (%)
	Skin and subcutaneous tissue disorders	n (%)
	Immune system disorders	n (%)
	Renal and urinary disorders	n (%)
	Cardiac disorders	n (%)
	Ear and labyrinth disorders	n (%)
	Investigations	n (%)
SAE	General disorders and administration site conditions	n (%)
	Vascular disorders	n (%)
	Eye disorders	n (%)
	Gastrointestinal disorders	n (%)

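### Safety aims are worded as absence of harm, yet adverse event percentages in ten patients carry no confidence limits; 0 of 10 is compatible with a true risk of up to 30.8%

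*SAP*

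**What the plan says.** **Objectives.** The aim in SAP section 1, shared with Protocol section 4.2, ends with "increasing tear production and improving quality of life with no adverse events". The secondary objectives (Protocol section 4.3.2, repeated in SAP section 1) end with "improve retinal perfusion and quality of life with no deleterious side effects". Both state safety as something that will not be seen.

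**Sample.** SAP section 5 says "Ten patients will be recruited". There is one arm and no control. For safety, the section claims only "further information on safety of ARA 290 in a diabetic population"; it gives no target precision and no event rate.

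**Analysis.** SAP section 6 says "Adverse events will be presented using counts and percentages", and Protocol section 12.3 agrees. SAP section 7.4 asks for number and percentage. The sentence on confidence intervals in SAP section 6 belongs to the preceding paragraph, on mean change in continuous outcomes, and gives no confidence level.

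**Tables.** Table 4.1 gives patient-level percentages for any adverse event, for serious adverse events ("Number of patients experiencing an SAE") and for deaths. Adverse reactions and serious adverse reactions appear there as event totals only. Table 4.2 does give patient-level numbers and percentages for adverse reactions and unexpected adverse reactions. No safety table has a place for an interval.

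**The concern.** An objective worded as absence, read against a bare percentage, makes a zero look like the objective met. With ten patients a zero says little about the underlying risk, and the plan has nothing that would show the reader how little.

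The exposure makes this more than a formality. Protocol section 3.3 says that treatment is extended to 84 days for the first time, from 28 days in most previous studies. The two earlier studies in diabetes or pre-diabetes that it describes gave the drug to 24 and 12 patients for 4 weeks. On what the documents report, evidence on weeks 5 to 12 in this population therefore comes mainly from these ten patients, and the results are meant to inform larger studies. A safety percentage without a limit could be carried forward as reassurance that it does not give.

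**Working it through.** **Inputs.** n = 10 (SAP section 5). All ten are taken as evaluable, because Protocol section 12.2 expects no drop-outs. The documents state no precision, power or detectable event rate for safety, so there is no figure of theirs to reproduce. The true risks of 5%, 10% and 15% below are illustrations and do not come from the documents.

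**1. Chance that a harm does not appear at all.** With true risk p per patient, P(0 of 10) = (1 − p)^10.
- p = 5%: 0.95^10 = 0.599, about 60%
- p = 10%: 0.90^10 = 0.349, about 35%
- p = 15%: 0.85^10 = 0.197, about 20%

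**2. What a zero count can exclude.** The exact (Clopper-Pearson) two-sided 95% upper limit U for a zero count solves (1 − U)^n = 0.025, so U = 1 − 0.025^(1/n).
- n = 10: U = 1 − 0.6915 = 0.308, or 30.8%
- n = 9: 33.6%
- n = 8: 36.9%

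**3. Low non-zero counts.** For x events the exact limits are the 0.025 quantile of Beta(x, n − x + 1) and the 0.975 quantile of Beta(x + 1, n − x).
- 1 of 10: 0.3% to 44.5%
- 2 of 10: 2.5% to 55.6%

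**4. Scale.** For a zero count to bring the two-sided 95% upper limit to 10% or below, n must be at least ln(0.025)/ln(0.9) = 35.01, that is 36 patients. This shows how far ten patients are from excluding a 1-in-10 risk. It is not a proposed sample size.

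**5. Does the interval sentence reach safety?** In SAP section 6 it follows the list of continuous outcomes and precedes the sentence on medians for non-normal data. The adverse event sentence opens the next paragraph and mentions only counts and percentages. The natural reading is that safety proportions get no interval. The table shells do not settle this: the efficacy shell, Table 3.1, also shows only mean and SD, although intervals are promised for those outcomes.

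**The case against.** The strongest reply is that nothing here is decided on a zero. The phrases in the aim and objective are loose wording tied to no test or threshold, the sample size section claims only "further information on safety of ARA 290 in a diabetic population", and the analysis is declared descriptive. That stands: the plan contains no safety criterion that could be met or failed.

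Safety is also not limited to percentages. Each event is assessed for seriousness, causality and severity, and for expectedness if related. Adverse events will be listed individually, and the data monitoring committee reviews safety about every 4 weeks. In ten patients, case-level review carries much of the information. This also stands, but none of it tells a reader what ten patients can exclude.

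The SAP was completed when some outcomes were known: section 6 says that no patient needed a week-16 visit, and Table 4.2 already names specific event terms. The zero-count problem therefore concerns serious events or a particular harm, not adverse events of any kind.

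Finally, the 35% follows from the sample size and an assumed risk, and an interval does not change it; any reader can compute a limit from x/10. True, but the plan offers intervals for continuous change scores and gives no reason for leaving them off safety. An interval is itself a description, so a descriptive analysis does not rule it out.

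**Conclusion.** The point holds as a cheap improvement in reporting, not as an error in the analysis. The safety aim is worded as absence, and the planned summary cannot show how weak a zero in ten patients is: the upper 95% limit is 30.8%. That limit assumes ten evaluable patients and independent binary outcomes with a common risk. The figures of 60%, 35% and 20% rest in addition on the illustrative risks.

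Three stronger readings are not supported.
- A reader might infer that the trial must see no adverse events to succeed, so that even an inert drug would fail. No section sets such a rule, and Protocol section 3.3 itself reports of earlier studies that "the frequency of adverse events was similar in both ARA 290 and placebo groups", so adverse events were expected without active drug.
- A reader might infer from Table 4.1 that adverse reactions are never counted by patient. Table 4.2 counts them; only serious adverse reactions lack a patient-level row.
- A reader might conclude that ten patients are too few for the stated purpose. The documents promise only further information on safety, and the gap is the missing statement of precision.

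**What to change.** 1. In SAP section 6 and Table 4.1, give exact (Clopper-Pearson) two-sided 95% limits for the patient-level proportions: any adverse event, any adverse reaction, any serious adverse event, any serious adverse reaction, and death. Use the number of evaluable patients as denominator and the same bound in table and text.
2. Add a patient-level row for serious adverse reactions to Table 4.1, and carry over the patient-level adverse reaction count from Table 4.2.
3. Restate the safety aim in SAP section 1 as estimating the proportions of patients with adverse reactions and with serious adverse events.
4. State that any zero count will be reported with its upper limit (0 of 10: up to 30.8%) and not as absence of harm.

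If the existing interval sentence was meant to cover safety, the SAP should say so and name the method and level. The cost is SAP and table wording and a few lines of code, with no new data. The downside is a safety statement that looks less favourable.
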